**7.3.6. *Discontinuation of the Study***

[figure not shown]
The study will be discontinued if Lilly judges discontinuation of the study necessary for medical, safety, regulatory, ethical, or other reasons consistent with applicable laws, regulations, and GCP.

## 8. Investigational Plan

### 8.1. Summary of Study Design

Study JPBQ is a multicenter, randomized, double-blind, Phase 3 trial for women with HR+, HER2- locoregionally recurrent or metastatic breast cancer.

Figure JPBQ.8.1 illustrates the study design.

Abbreviations: HER2- = human epidermal growth factor receptor 2-negative; HR+ = hormone receptor-positive; mBC = metastatic breast cancer; N = number of planned patients; NSAID = nonsteroidal aromatase inhibitor; R = randomization

a The initiation of enrollment for patients in Cohort B was triggered later according to Lilly global strategy.

**Figure JPBQ.8.1. Illustration of study design.**

The study will consist of 2 patient cohorts:

- Cohort A will include approximately 300 patients with HR+, HER2- locoregionally recurrent or metastatic breast cancer who meet Inclusion Criterion 2a (Section 7.1).
- Cohort B will additionally include approximately 150 patients with HR+, HER2- locoregionally recurrent or metastatic breast cancer who meet Inclusion Criterion 2b (Section 7.1). The initiation of enrollment for patients in Cohort B was triggered later according to Lilly global strategy.

Patients in each cohort will be randomized 2:1 between the experimental and control arms:

- Arm A1: Abemaciclib 150 mg orally Q12H on Days 1 to 28 plus either anastrozole 1 mg or letrozole 2.5 mg orally Q24H of a 28-day cycle
- Arm A2: Placebo orally Q12H on Days 1 to 28 plus either anastrozole 1 mg or letrozole 2.5 mg orally Q24H of a 28-day cycle
- Arm B1: Abemaciclib 150 mg orally Q12H on Days 1 to 28 of a 28-day cycle plus fulvestrant 500 mg intramuscularly on Days 1 and 15 of Cycle 1, then on Day 1 of Cycle 2 and beyond
- Arm B2: Placebo orally Q12H on Days 1 to 28 of a 28-day cycle plus fulvestrant 500 mg intramuscularly on Days 1 and 15 of Cycle 1, then on Day 1 of Cycle 2 and beyond

Patients in Cohort A will be randomized using the following stratification factors: nature of disease (visceral metastases vs. non-visceral metastases) and prior (neo)adjuvant endocrine therapy (prior therapy with disease-free interval > 12 months from completion of treatment vs. prior therapy with disease-free interval ≤ 12 months from completion of treatment vs. no prior endocrine therapy). The presence of visceral metastases refers to lung, liver, pleural, peritoneal, or adrenal gland involvement at the time of randomization.

Patients in Cohort B will be randomized using the following stratification factors: nature of disease (visceral metastases vs. non-visceral metastases) and sensitivity to endocrine therapy (primary resistance vs. secondary resistance). The presence of visceral metastases refers to lung, liver, pleural, or peritoneal, or adrenal gland involvement at the time of randomization. Primary clinical resistance to endocrine therapy is defined as follows: 1) for endocrine therapy in the adjuvant setting, recurrence within the first 2 years of adjuvant endocrine therapy while on endocrine therapy, or 2) for endocrine therapy in the locoregionally recurrent or metastatic setting, progression within first 6 months of initiating first-line endocrine therapy while on endocrine therapy. Patients receiving prior endocrine therapy who do not meet the definition of primary clinical resistance will be considered to have secondary clinical resistance.

The primary analysis of the PFS endpoint will occur after approximately 170 PFS events have been observed in Cohort A. An interim analysis will be conducted after approximately 119 PFS events are observed to provide early efficacy information and allow for potential early communication with regulatory agencies. (see Section 12.2.6 for details).

The interim analysis of Cohort B will follow the timeline of Cohort A, which will occur only if the interim of Cohort A turns out to be positive. If patients in Cohort A continue being followed for PFS until final analysis, the final analysis of Cohort B will be conducted at the same time of Cohort A final analysis. If Cohort A stops early at interim due to efficacy, the final analysis of Cohort B may be conducted after approximately 105 PFS events have been observed in Cohort B. (see Section 12.2.14 for details).

For each cohort, all patients will be followed for progression and survival information until death or study completion, whichever occurs first.

Terms used to describe the periods during the study are defined below:

- **Baseline:** begins when the informed consent form (ICF) is signed and ends at the first study treatment dose (or at discontinuation, if no treatment is given). This may be up to 28 days prior to the first study treatment dose.
- **Study Period:** begins at the first study treatment and ends at study completion. The study period does not include the continued access period.
  - **Study Treatment Period:** begins at the first study treatment and ends when the patient and the investigator agree that the patient will no longer continue study drug. The date of this agreement is to be reported on the electronic case report form (eCRF) as the Date of Discontinuation from study drug.
  - **Postdiscontinuation Follow-Up:** begins the day after the patient and the investigator agree that the patient will no longer continue study drug.

*Short-term follow-up* begins the day after the patient and the investigator agree that the patient will no longer continue study drug and lasts approximately 30 days ( $\pm 7$  days).

[figure not shown]
*Long-term follow-up* begins the day after short-term follow-up is completed and continues until the patient's death or overall study completion, whichever comes first.

- **Continued Access Period:** begins after study completion and ends at the end of trial. During the continued access period, patients on study treatment who continue to experience clinical benefit may continue to receive study treatment until one of the criteria for discontinuation is met.
  - The continued access period includes continued access period short-term follow-up.
  - Continued access short-term follow-up: begins the day after the patient and the investigator agree that the patient will no longer continue treatment in the continued access period and lasts approximately 30 days.

### **8.1.1. Study Completion and End of Trial**

This study will be considered complete following the last required PFS event from Cohort A (Figure JPBQ.8.2), as determined by Lilly. In case Cohort A stops early at interim due to efficacy and Cohort B continues thereafter, Cohort B will be considered complete following the final analysis of PFS in Cohort B. Investigators will continue to follow the study schedule for all patients until notified by Lilly that study completion has occurred.

The end of trial occurs after study completion and after the last patient has discontinued study treatment and completed any applicable continued access follow-up.

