legal representative	An individual, judicial, or other body authorized under applicable law to consent on behalf of a prospective patient to the patient's participation in the clinical study.
Lilly Safety System	Global safety database that tracks and reports serious adverse and spontaneous events occurring while using a drug/drug delivery system.
LLT	Lower Level Term
mBC	metastatic breast cancer
mBPI-sf	modified Brief Pain Inventory short form
MedDRA	Medical Dictionary for Regulatory Activities
MRI	magnetic resonance imaging
mRNA	messenger ribonucleic acid
NCI	National Cancer Institute
NSAI	nonsteroidal aromatase inhibitor
OS	overall survival
patient	A study participant who has the disease or condition for which the investigational product is targeted.
PD	progressive disease
PET	positron emission tomography

PFS	progression-free survival
PgR	progesterone receptor
PK	pharmacokinetic(s)
PR	partial response
PRO	patient-reported outcome
PS	performance status
PT	Preferred Term
Q12H	every 12 hours
Q24H	every 24 hours
QTc	corrected QT interval
randomize	the process of assigning patients to an experimental group on a random basis
RANK-L	RANK ligand
Rb	retinoblastoma
RECIST	Response Evaluation Criteria in Solid Tumors
reporting database	A point-in-time copy of the collection database. The final reporting database is used to produce the analyses and output reports for interim or final analyses of data.
re-screen	to screen a patient who was previously declared a screen failure for the same study
SAE	serious adverse event
SAP	Statistical Analysis Plan
screen	The act of determining if an individual meets minimum requirements to become part of a pool of potential candidates for participation in a clinical study
screen failure	patient who does not meet one or more criteria required for participation in a trial
SD	stable disease
SMD	Senior Management Designee
SOC	System Organ Class
study completion	This study will be considered complete, following the last required PFS event from Cohort A or Cohort B, whichever is longer, as determined by Lilly, when all of the required short-term follow-up assessment is completed.
SUSAR	suspected unexpected serious adverse reaction

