**Figure JPBQ.8.2. Study period and continued access diagram.**

### **8.1.2. Continued Access Period**

After study completion, all patients who are on study treatment and who are eligible for continued access will be unblinded. Patients receiving study treatment and experiencing ongoing clinical benefit and no undue risks may continue to receive study treatment in the continued access period until one of the criteria for discontinuation is met (see Section 7.3). Lilly will notify investigators when the continued access period begins.

Long-term follow-up does not apply in the continued access period.

Patients who are in long-term follow-up when the continued access period begins will be discontinued from long-term follow-up.

During the continued access period, all AEs, SAEs, and study drug exposure will be reported on the case report form (CRF). Serious adverse events will also be reported to Lilly Global Patient Safety (see Section 10.3.1). In the event that an SAE occurs, Lilly may request additional information (such as local laboratory results, concomitant medications, and hospitalizations) in order to evaluate the reported SAE.

Investigators will perform any other standard procedures and tests needed to treat and evaluate patients; however, the choice and timing of the tests will be at the investigator's discretion. Lilly will not routinely collect the results of these assessments.

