## **9.5. Blinding**

This is a double-blind study.

To preserve the blinding of the study, a minimum number of Lilly personnel will see the randomization table and treatment assignments before the study is complete. Access to unblinded data/documents will be controlled by restricting access to the data/documents in Lilly's data and statistical warehouse. Any changes to this unblinding plan may be described in a protocol amendment, the Statistical Analysis Plan (SAP), and/or a separate unblinding plan document.

Efficacy information will not be shared between sites until the study is completed. Upon overall study completion (see Section [8.1.1](#)), investigators may unblind patients to study treatment assignment.

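### If Cohort A stops at its interim, is study completion so unclear that the final OS analysis has no fixed cut-off?

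*Protocol*

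**What the plan says.** The Protocol defines study completion in two places.

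- Section 4 (Abbreviations and Definitions): the study is complete "following the last required PFS event from Cohort A or Cohort B, whichever is longer", as determined by the sponsor, "when all of the required short-term follow-up assessment is completed".
- Section 8.1.1: "This study will be considered complete following the last required PFS event from Cohort A". For an early stop it continues: "In case Cohort A stops early at interim due to efficacy and Cohort B continues thereafter, Cohort B will be considered complete" once Cohort B's final PFS analysis is done. It then keeps investigators on the study schedule, for all patients, until the sponsor tells them the study is complete.

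Several rules depend on this term.

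- Follow-up (Section 8.1): "For each cohort, all patients will be followed for progression and survival information until death or study completion, whichever occurs first".
- Continued access (Section 8.1.2): "After study completion, all patients who are on study treatment and who are eligible for continued access will be unblinded", and "Patients who are in long-term follow-up when the continued access period begins will be discontinued from long-term follow-up".
- Blinding (Section 9.5): at overall study completion, "investigators may unblind patients to study treatment assignment".
- OS (Protocol 12.2.7.2 and SAP 6.7.2.2): the final analysis takes place with the PFS analysis at study completion. The SAP adds 1-year and 2-year survival rates for each cohort.

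Protocol 12.2.14 and SAP 6.13 plan about 170 Cohort A events if the interim is not significant. If it is significant, the sponsor may consider stopping, unblinding and crossover for Cohort A after consulting regulators. Cohort B's final analysis may then come at about 105 of its own events.

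**The concern.** Read literally, the two definitions separate on the early-stop branch. No further Cohort A event is then required, so Section 8.1.1 could place completion at event 119, while Section 4 would place it at Cohort B's last required event. No sentence states when the whole study is complete on that branch.

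Two things would be at stake. A cut at event 119 gives short survival follow-up, and the 2-year OS rate in Cohort A, a listed secondary objective, may not be estimable. A later cut gives more follow-up but includes control patients who crossed over. A sponsor choosing between these after seeing the interim would be choosing the OS analysis post hoc. Completion at event 119 would also trigger unblinding under Sections 8.1.2 and 9.5 while Cohort B was still being followed.

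**Working it through.** **Inputs from the documents.** 300 patients in Cohort A, 200 and 100 by arm; control median PFS 14.4 months, exponential; hazard ratio 0.626; looks at 119 and 170 events; one-sided boundaries p < 0.0082 and p < 0.0223 (Protocol 12.1 and 12.2.6).

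**Plan's own figures.** A two-look bivariate normal calculation with those boundaries gives power 81.41% (stated 81.40%) and one-sided alpha 0.0250. The interim hazard-ratio bound is exp(−2.400/√(119 × 2/9)) = exp(−2.400/5.142) = 0.627, as stated. Censoring at the final look is 1 − 170/300 = 43%, as stated.

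**Chance of crossing at event 119.** Φ(ln(1/HR) × √(119 × 2/9) − 2.400).

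- HR 0.626: 0.4684 × 5.142 = 2.409, and Φ(0.009) = 50%.
- HR 0.70: 0.3567 × 5.142 = 1.834, and Φ(−0.566) = 29%.

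**Timing of the looks.** Accrual length is not in the documents, so uniform accrual over A months is an assumption. Hazards are ln 2/14.4 = 0.0481 (control) and 0.626 × 0.0481 = 0.0301 (abemaciclib) per month. For T ≥ A and no dropout, expected events at month T are the sum over arms of n × [1 − (e^(−λ(T−A)) − e^(−λT))/(λA)]. For A = 12 and T = 20.4 this is 69.7 + 49.3 = 119.0. The share of patients with 24 months since randomization is max(0, (T − 24)/A).

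| Assumed accrual (months) | Event 119 (month) | Patients with ≥ 24 months | Event 170 (month) | Patients with ≥ 24 months |
|---|---|---|---|---|
| 6 | 17.2 | 0 | 26.7 | 136 |
| 12 | 20.4 | 0 | 29.9 | 147 |
| 18 | 23.7 | 0 | 33.2 | 153 |
| 24 | 27.1 | 38 | 36.5 | 157 |

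Calibrating accrual so that event 170 falls at month 33 (October 2016 to July 2019) gives 0 of 300 at event 119. Calibrating to the stated 38 months gives A = 26.5, event 119 at month 28.5, and (28.5 − 24)/26.5 = 17%, or 51 of 300. With an assumed dropout hazard of 0.01 per month, the four interim counts become 0, 0, 20 and 58. So the loss of the 2-year rate is real under an event-119 cut with fast accrual. The remaining question is whether the plan means that cut.

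**The definitions, branch by branch.**

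1. *Cohort A followed to its final analysis.* Cohort B is analysed at the same time (Protocol 8.1, 12.2.7.1, 12.2.14) and has no event target of its own. Both definitions then point to Cohort A's last required event. They differ only in Section 4's short-term follow-up clause, about 30 ± 7 days.
2. *Cohort A stopped early.* Section 4 gives Cohort B's last required event. The early-stop sentence in 8.1.1 completes Cohort B at its final PFS analysis, which that event triggers. Event 119 emerges only if the first sentence of 8.1.1 is read without the second. A study with a cohort still under follow-up is not complete in any ordinary sense.

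**Other text on the early-stop branch.** Under 8.1.1 the schedule continues for all patients, not just Cohort B, until a study-level notice. Section 9.5 speaks of overall study completion. Section 12.2.14 treats unblinding after a significant interim as a decision for the cohort concerned. Section 10.1.2 says survival data continue to be collected on all patients.

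**The case for a change.** The strongest case for acting is that both definitions are current text, that no sentence names study-level completion on the early-stop branch, and that the date is left to the sponsor. Section 10.1.2 on continued survival collection gives no end date, and Section 8.1.2 removes patients from long-term follow-up once continued access begins. The SAP uses the term without defining it. A short clarification written before the interim would cost little and would prevent a post hoc choice of OS cut-off.

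Part of this stands. The Section 4 entry does not match 8.1.1. The amendment (e) summary in Attachment 10 shows why: the whichever-is-longer and short-term follow-up wording was removed from 8.1.1, and the glossary was not updated. That is a clerical slip. The date of Cohort B's 105th event also cannot be derived, because neither its control median nor its start date is given. The natural reading therefore gives a cut-off no earlier than the interim, but by how much is unknown.

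The rest does not carry far enough. Asking the plan to name a cut-off settles nothing about which is better: the earlier one gives immature OS, and the later one gives OS that includes crossover. Neither dominates. OS has no alpha allocated and is described by Kaplan-Meier and Cox estimates. A survival rate at a time the curve has not reached is simply reported as not estimable, and a minimum-at-risk rule for it would be a matter of preference.

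**Conclusion.** No change follows. The two definitions share a PFS trigger whenever Cohort A runs to its final analysis. If Cohort A stops early, the sensible reading is that the study completes with Cohort B's final PFS analysis, and analysts would cut OS there.

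The 2-year OS rate in Cohort A is at risk only if three things hold together: the interim is significant, the sponsor then chooses to stop, and completion is read as event 119. Even then, at the design hazard ratio without dropout, it is lost outright only with assumed accrual up to about 18 months; at the Synopsis's 38-month length about 51 of 300 patients would have 24 months since randomization. The 50% is the chance of crossing the boundary at a hazard ratio of 0.626 (29% at 0.70), not the chance of an early stop.

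The primary PFS analysis, event counts and alpha are unaffected. This rests on uniform accrual and exponential PFS as assumed above, and on the text alone: Figure JPBQ.8.2, which 8.1.1 cites for the completion rule, was not visible.

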**Figure JPBQ.8.2. Study period and continued access diagram.**

### **8.1.2. Continued Access Period**

After study completion, all patients who are on study treatment and who are eligible for continued access will be unblinded. Patients receiving study treatment and experiencing ongoing clinical benefit and no undue risks may continue to receive study treatment in the continued access period until one of the criteria for discontinuation is met (see Section 7.3). Lilly will notify investigators when the continued access period begins.

Long-term follow-up does not apply in the continued access period.

Patients who are in long-term follow-up when the continued access period begins will be discontinued from long-term follow-up.

During the continued access period, all AEs, SAEs, and study drug exposure will be reported on the case report form (CRF). Serious adverse events will also be reported to Lilly Global Patient Safety (see Section 10.3.1). In the event that an SAE occurs, Lilly may request additional information (such as local laboratory results, concomitant medications, and hospitalizations) in order to evaluate the reported SAE.

Investigators will perform any other standard procedures and tests needed to treat and evaluate patients; however, the choice and timing of the tests will be at the investigator's discretion. Lilly will not routinely collect the results of these assessments.

## 8.2. Discussion of Design and Control

A randomized, controlled design is being used in this study. Randomization minimizes systematic bias in the selection and assignment of patients to study therapy and provides justification for inferential statistical methods to be used on data from this study. Using an appropriate concurrent control arm enables direct statistical estimation of benefits and harms due to study therapy and minimizes bias in the assessment and interpretation of observed treatment effects. Patients will be stratified for differences in factors thought to be associated with clinical outcomes to further reduce the potential for bias and improve the power of the analyses. Assessment of bias is further minimized by the use of a double-blind placebo control (see Section 9.3).

Investigational treatment administration in this study is double-blind; that is, patients, investigational sites, and the sponsor study team do not have immediate access to investigational treatment assignments for any patients. This design feature minimizes potential bias due to knowledge of patient's treatment during evaluation of study endpoints, at the patient level or aggregated across patients.

The 4-arm design of this study will allow 2 investigations in 1 specific population (ie, HR+, HER2- locoregionally recurrent or metastatic breast cancer). Patients in different cohorts will receive 2 standard endocrine therapies with or without abemaciclib, based on prior treatments and associated outcome, respectively. Furthermore, this design allows descriptive comparison of safety between different combinations or potential pooled analysis within the same setting by eliminating cross-trial confounders and following a consistent data collection plan.

## 9. Treatment

### 9.1. Treatments Administered

The following treatments will be administered in this study:

- Arm A1: Abemaciclib 150 mg orally Q12H plus either anastrozole 1 mg or letrozole 2.5 mg orally Q24H on Days 1 to 28 of a 28-day cycle.
- Arm A2: Placebo orally Q12H plus either anastrozole 1 mg or letrozole 2.5 mg orally Q24H on Days 1 to 28 of a 28-day cycle.
- Arm B1: Abemaciclib 150 mg orally Q12H on Days 1 to 28 of a 28-day cycle plus fulvestrant 500 mg intramuscularly on Days 1 and 15 of Cycle 1, then on Day 1 of Cycle 2 and beyond
- Arm B2: Placebo orally Q12H on Days 1 to 28 of a 28-day cycle plus fulvestrant 500 mg intramuscularly on Days 1 and 15 of Cycle 1, then on Day 1 of Cycle 2 and beyond

Blinded study drug is defined as abemaciclib or placebo. Study treatment is defined as blinded study drug and/or NSAI/fulvestrant.

The specific NSAI (anastrozole or letrozole) administered to patients in Cohort A is determined by the investigator. Patients should remain on the same NSAI throughout the study. In exceptional cases, in the absence of evidence of PD, the investigator may discuss a change in NSAI with the Lilly CRP. Nonsteroidal aromatase inhibitor is a co-administered standard-of-care treatment. The investigator should refer to the NSAI label (ie, Patient Information Leaflet, Package Insert, or Summary of Product Characteristics).

Fulvestrant 500 mg should be administered intramuscularly into the buttocks of patients in Cohort B slowly (1 to 2 minutes per injection) as two 250-mg injections, one in each buttock; however, for patients with moderate hepatic impairment (defined as Child-Pugh Class B), including any patient who develops moderate hepatic impairment during study treatment, fulvestrant 250 mg should be administered intramuscularly into the buttock slowly (1 to 2 minutes) as one 250-mg injection. Fulvestrant is a co-administered standard-of-care treatment. The investigator should refer to the fulvestrant label (ie, Patient Information Leaflet, Package Insert, or Summary of Product Characteristics).

[Table JPBQ.9.1](#) shows the treatment regimens.

